Glucose meter and insulin rate reporting: The research assistant will provide instructions for the participant to report readings from their diabetes devices. For continuous glucose sensor and insulin pump users, device data for the past month will be provided through data exports from the device software for sharing with healthcare teams, with no medical device ID or personal identifiers retained. For glucose meter users, they will report glucose readings for the last 7 days from their glucose meter. For insulin injection users, they will report long-acting insulin doses and carbohydrate exchange ratios used over the last 7 days.

As the final activity of the baseline assessment, the participants will be randomized to the Activate program or treatment-as-usual and receive instruction, if required on completing the intervention program, and for all the follow-up assessment.

After twelve weeks, adolescents and their primary caregiver will repeat the entire baseline assessment battery in a second video-based lab appointment. Adolescents will receive \$25 for the intake assessment and \$50 for the follow-up assessment on a study provided cash card or gift card. Adolescents will return the assessment toolkit with a pre-paid mailing label.

Intervention: Activate Program

Adolescents randomized to the active condition will participate in a 12-week online diabetes behavior-change skills training and physical activity promotion program. See attached intervention guide for protocols beyond description below.

Diabetes Behavior-Change Skills Training. Behavior-change skills training will be provided through eight web-delivered content and activity sessions across the 12-week program. Sessions 1 through 4 will occur weekly and sessions 5 through 8 biweekly. Each session takes approximately 15-20 minutes for the adolescent to complete both content learning and related activities. Session 1 (week 1 of program) provides an introduction to the entire Activate Program as well as a goal-setting activity related to type 1 diabetes management. Sessions 2-8 (weeks 2 to 12 of the program) provide physical activity reminders that overlap with text-based support for the physical activity program (see below) as well as specific session content for behavior-change skills training: goal setting, goal planning and rewards, identifying challenges, problem-solving, increasing social support and positive activities, and managing strong emotions.

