Physical Activity Incentives Program. The physical activity incentives program includes 12 weeks of personalized goals and incentives for increasing physically active minutes along with weekday text-based support. Active minutes, defined as minutes with moderate to vigorous physical activity, will be tracked via a Garmin fitness activity tracker, which is synced to a coded study-specific account via PhysioQ's Labfront, a secure site used to collect and manage Garmin fitness activity tracker data. All data will be deidentified and only accessible to the research team. In week 1, all adolescents will receive incentives for syncing their Garmin fitness activity tracker on at least five days. In weeks 2 to 12, adolescents will receive personalized daily and weekly activity goals based on their progress. Daily incentives will be offered for meeting daily goals, and increased earnings will be available for meeting weekly bonus goals. Maximum earnings across the 12 weeks will be \$430. Weekdays, text-based support will be provided to remind adolescents of goals and earning potential as well as additional support to problem-solve technology and physical activity difficulties when indicated. Education prior to the intervention will follow American Diabetes Association³¹ guidance including information about how insulin requirements change with increased physical activity and how to prevent hypo and

hyperglycemia during and after exercise as well as reviewing the adolescent's plans for managing low blood glucose and contacting their pediatric endocrinologist with questions about glucose management with increased physical activity. All incentives will be delivered weekly on a cash card provided by the study or via gift card(s) provided at an interval chosen by the participant.

Treatment-as-Usual Control condition. For those in treatment as usual, participants will be trained to wear a Garmin fitness activity tracker daily for the next 12 weeks and asked to follow their standard care for diabetes management.

Describe required screening procedures performed before enrollment and while on study.

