Contact between potential participants and study personnel will be initiated by the potential participants and their caregivers. Potential participants and their caregivers will respond to internet or clinic-provided advertisements and will be routed to our study website. Our study website will contain a description of study procedures and link to request contact regarding study participation. A research assistant will return contact with interested families to answer questions about the study and confirm eligibility using the screening consent script and set a date/time for consent/assent. Inclusion criteria will be the adolescents aged 13-17, and not turning 18 during study participation, with type 1 diabetes, being at least 18 months post-diagnosis, parent reported moderate to no physical activity for adolescent, ability to complete measures and intervention program in English, and access to broadband or cellular internet and currently residing in and receiving healthcare in the United States. After 30 participants are consented and enrolled into the study, we will add the following inclusion criteria: adolescent is from a marginalized racial or ethnic group. Exclusion criteria will be ward of state, active psychosis, and/or severe medical or psychiatric illness that limit participation including participation in physical activity. Participants will be provided contact information for the PI and lab to communicate during the 12-week study period about any concerns for eligibility (e.g., loss of internet, change in legal guardian status) and the PI will evaluate continued participation based on confirmation of meeting eligibility requirements.

For research involving survey, questionnaires, etc.: Describe the setting and the mode of administering the instrument and the provisions for maintaining privacy and confidentiality. Include the duration, intervals of administration, and overall length of participation.

Not applicable

Each assessment will be scheduled for a three-hour window to complete the questionnaires (80 minutes), the physical assessments (dried blood spot, abdominal circumference, blood pressure, and diabetes device reporting; 40 minutes), and at intake introduction to the treatment condition (20 minutes). Each assessment appointment is anticipated to last 2.5-3 hours.

Primary Outcomes

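### The Protocol lets the PI decide continued participation on entry criteria after randomisation, with no rule that keeps the affected adolescents in follow-up and analysis

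*Protocol*

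**What the plan says.** - **Timing (Protocol, Procedures).** "As the final activity of the baseline assessment, the participants will be randomized to the Activate program or treatment-as-usual". The 12-week period therefore lies wholly after allocation.
- **Reporting route (Protocol, screening before enrollment and while on study).** "Participants will be provided contact information for the PI and lab to communicate during the 12-week study period". The matters to be raised are doubts over whether the adolescent is still eligible; a lost connection and a new guardian are the two examples given. The route is the same for both arms and depends on the family making contact.
- **Decision (same section).** "the PI will evaluate continued participation based on confirmation of meeting eligibility requirements". The section does not say which requirements are confirmed again, whether follow-up continues if one is no longer met, or whether the PI is masked to arm.
- **Entry criteria (same section).** These include internet access and "parent reported moderate to no physical activity for adolescent".
- **Withdrawal (Protocol, Withdrawal Procedures).** The team does not expect to withdraw anyone but keeps the right to do so. Data from anyone who leaves or is withdrawn are omitted from the analyses.
- **Analysis.** Protocol Statistical Considerations analyses everyone, with full information maximum likelihood (FIML) for missing data. The SAP also analyses everyone, but sets missing data to zero.

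**The concern.** Eligibility normally settles who is randomised. Here it also governs who stays in, on the basis of events that happen later. Loss of internet is not a neutral event in this trial. The program consists of "eight web-delivered content and activity sessions across the 12-week program" plus weekday texts and tracker-based incentives, and it is aimed at adolescents with socioeconomic disadvantage. A family that loses its connection shows one way the program can fail in use.

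Two results are exposed. The acceptability benchmarks in Statistical Considerations (more than 80% of sessions completed and activity goals met, more than 80% willing to take part again) could look better than they should. The between-arm comparison of active minutes and the other outcomes could lose the protection of randomisation. If ending participation also means no week-12 visit, the outcome is never measured, and any analysis rule can then only assume it or discard it.

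**Working it through.** **1. Which criteria count.** The two named triggers are examples, so the list is open. Read literally, the requirements include low to moderate activity at entry, which Activate aims to change. Removing adolescents who became more active would pull the estimated effect down. Excluding those who lost access and gained nothing would push it up. The direction is therefore not fixed by the text.

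**2. What happens to the data.** Withdrawal Procedures omits withdrawn participants. Statistical Considerations keeps everyone and uses FIML. The SAP keeps everyone and fills in zero. These three rules cannot all apply to the same adolescent.

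**3. Acceptability benchmark (illustration).** Assume 30 adolescents in Activate, of whom 27 complete 85% of sessions on average and 3 lose internet and complete 25%.
- All 30 in the denominator: (27 × 85 + 3 × 25)/30 = 2370/30 = 79%, benchmark missed.
- The 3 left out: 85%, benchmark met.

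This needs no difference between arms. It does need the 3 to leave the denominator, on which the documents are silent.

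**4. Effect estimate (illustration).** Assume 30 per arm, k Activate adolescents who gain nothing, an equal gain g in the other 30 − k, no gain in controls and an unchanged SD. The full-sample effect is E = (30 − k)g/30.
- *Excluded:* the estimate is g = E × 30/(30 − k).

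| k | 30/(30 − k) | a d of 0.70 becomes |
|---|---|---|
| 2 | 1.07 | 0.75 |
| 3 | 1.11 | 0.78 |
| 4 | 1.15 | 0.81 |

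- *Zero entered as the gain:* ((30 − k)g + 0)/30 = E, so no inflation.
- *Zero entered as week-12 minutes:* the Activate mean falls below its true value and the estimate drops below E.
- *FIML:* the result depends on how well baseline and the disease covariates explain who loses access, which the documents cannot tell us.

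Removing k similar controls as well leaves the control mean at zero, so the factor is unchanged. It comes from dropping Activate adolescents who did not gain, not from unequal detection between arms.

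**5. Bias with no true effect.** A 20,000-run simulation removed the lowest k of 30 Activate adolescents on a trait correlated rho with the outcome, excluded them, and removed no controls.

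| k removed | rho | bias toward Activate (SD) | type I error |
|---|---|---|---|
| 3 | 0.3 | 0.06 | 5.6% |
| 3 | 0.5 | 0.10 | 6.7% |
| 6 | 0.3 | 0.10 | 6.2% |
| 6 | 0.5 | 0.17 | 9.3% |

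With rho = 0, or with 3 removed from each arm, the bias is about zero.

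**6. Power.** The plan puts no figure on these removals. Its nearest figure is 80% power at d = 0.7 with 60 participants. A two-sided 5% t test with 30 per arm (alpha and allocation ratio are assumed, since neither is stated) gives 76.0%, so the stated figure is not reproduced; nothing here depends on that. With 27 against 30 the power is 73.6%, and with 24 against 30 it is 70.8%.

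**The case against.** The strongest reply is that the text says evaluate, not remove. No re-check is scheduled, and Withdrawal Procedures expects no withdrawals. Under the screening section cellular access is enough (the Inclusion/Exclusion Criteria section mentions broadband only), and Procedures supplies tablets to families without a device. A guardian change is largely a matter of permission, and wards of the state are excluded anyway. The Protocol's text on stopping rules also commits the team to watch for patterns in attrition and feasibility. All of this stands and keeps the point small. It does not supply the missing rule: the only stated basis for the PI's decision is whether eligibility requirements are met, and nothing says that follow-up continues if they are not.

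A reader might also infer that losses would be detected mainly in Activate, which has web sessions, weekday texts and technology support, and that the arms would therefore become unbalanced. Some asymmetry for internet loss is plausible, but the documents do not show it. The reporting route is the same in both arms. Under Compensation, controls are paid $0.50 per day of tracker wear up to $42, which is 84 days or the full 12 weeks, so the team must obtain their wear data too. Nothing suggests that guardian changes are noticed more in one arm.

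A second tempting inference is that adolescents who become active would be removed for no longer meeting the activity criterion. The wording does not rule this out, but both examples concern access and legal status, and nothing says that the criterion would be used this way.

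**Conclusion.** The point holds as a gap in the rules, of minor severity. Continued participation after randomisation is tied to entry criteria, the list of criteria is open, and the Protocol and SAP disagree on whether anyone removed is analysed. Bias in the acceptability result and in the between-arm comparison is possible.

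Its size cannot be derived, because the documents give no expected number of such events. The 7%, 11% and 15% figures assume 30 per arm, no gain in those removed or in controls, and exclusion from the analysis. They do not carry over to zero-filling and are not evidence of unequal detection. The simulated bias rests on assumed removal counts and correlations, and disappears when removals are balanced or unrelated to outcome.

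**What to change.** Replace the sentence on continued participation with wording such as:

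> Eligibility is determined once, before randomization. Later loss of an entry criterion is recorded with its date, reason and study arm, and does not by itself end follow-up. The participant remains in the assigned arm, is invited to the 12-week assessment, and stays in the acceptability denominators and the analysis. After a change of legal guardian, participation continues subject to the new guardian's permission and applicable IRB requirements. Safety-based withdrawal is governed by a separate rule.

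Then reconcile the data-exclusion sentence in Withdrawal Procedures with Statistical Considerations and the SAP, so that one rule covers participants whose participation ends early. The change concerns follow-up and analysis and leaves the content of the safety rule to the investigators.

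The cost is a wording amendment and, for a few adolescents, a loaned tablet or renewed permission for the week-12 visit. Tablets are already provided for under Procedures.

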20. Type 1 Diabetes Quality of Life (T1DAL)³⁹, which includes 23 items that measure diabetes-related quality of life which is associated with treatment engagement and glycemic outcomes.

Secondary Health Outcomes

Inflammation. We will assess a primary marker of inflammation, c-reactive protein, through dried blood spot assay (see protocol above). Elevated c-reactive protein is associated with increased risk for atherosclerosis, endothelial dysfunction, and risk for cardiovascular disease.

Glycemic Outcomes. We will use the following measures to assess glycemic outcomes:

21. Glycated Hemoglobin (HbA1c) will be assessed through dried blood spot assay.
22. Mean Daily Blood Glucose (MBG) and Mean Variability in Blood glucose will be assessed by participant report from diabetes device data from glucose meters and CGMs. This will include data from the 7 days prior to the baseline assessment and 7 days prior to the follow-up assessment and will be used to index MBG and standard deviations in blood glucose levels (SDBG), both of which are available without requiring CGM. For those with CGM we will also examine time-in-range.
23. Insulin Resistance will be assessed by the estimated glucose disposal rate (eGDR) calculated from abdominal circumference and blood pressure measures at baseline and follow-up assessments (see protocol above).
24. **Insulin Needs:** Self-perceived insulin needs will be assessed using a single Likert scale question asking how the parent believes the teen's insulin needs have changed over the last 12 weeks (decreased greatly – increased greatly). This question will only be asked in the follow-up appointment after the 12 weeks. Parents will report on this measure.

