To assess the preliminary efficacy of the Activate program we will examine changes in proximal primary outcomes of goal-setting, coping skill efficacy, and average daily active minutes compared between treatment and control groups at baseline and the 12-week follow-up assessment. We will conduct multilevel models with baseline-residualized gain scores for outcomes to identify the effect size for the treatment program on each of the three primary outcomes. Each model will include the baseline outcome covariate as well as additional disease covariates including diabetes technology use and length of diagnosis. All participants will be used in analyses, with missing data addressed with full information maximum likelihood estimation. A power sensitivity function was generated wherein our pilot study analyses were used to determine expected effect sizes. Anticipated effect sizes based on our pilot work for between group differences in behavior-change skills and average daily active minutes are Cohen's d of 0.4 to 1.2. With 60 participants, we will have 80% power to detect a Cohen's d of .7, 60% power to detect a Cohen's d of .6, at 95% power to detect a Cohen's d of .8. Thus, we will be powered to detect all but the smallest of potentially meaningful effects found in our previous intervention pilot work.

In aim 2, we test the impact of the Activate program on secondary mechanisms of biobehavioral self-regulation systems and glycemic and cardiovascular disease risk outcomes closely linked with type 1 diabetes health disparities. To assess changes in putative mechanisms and secondary outcomes we will use baseline-residualized gain scores in multilevel models to identify the effect size for the treatment program on each of the secondary outcomes assessed for behavior regulation, distress, c-reactive protein, mean and variability in daily blood glucose, and cardiovascular disease risk score. For all analyses missing data will be addressed with full information maximum likelihood estimation. A power sensitivity function was generated wherein our pilot study analyses were used to determine expected effect sizes. Based on our pilot work we anticipate effect sizes from Cohen's d of .4 to .8 and thus with 60 participants, we will again have 80% power to detect a Cohen's d of .7, 60% power to detect a Cohen's d of .6, at 90% power to detect a Cohen's d of .8. We will be powered to detect all but the smallest of potentially meaningful effects found in our pilot work.

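### Glucose variability is indexed only by the SD, so if the SD moves with the mean, a change in mean glucose could be partly counted again as a change in variability

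*Protocol*

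**What the plan says.** Item 22 of the Protocol (Secondary Health Outcomes, Glycemic Outcomes) names two measures from one source: "Mean Daily Blood Glucose (MBG) and Mean Variability in Blood glucose will be assessed by participant report from diabetes device data". The window is the "7 days prior to the baseline assessment and 7 days prior to the follow-up assessment", and those readings "will be used to index MBG and standard deviations in blood glucose levels (SDBG". No coefficient of variation (CV) or other index that standardizes spread for level is named. One further measure is added for part of the sample: "For those with CGM we will also examine time-in-range".

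The Aim 2 paragraph of Statistical Considerations lists "c-reactive protein, mean and variability in daily blood glucose, and cardiovascular disease risk score" among the outcomes. The models are to "identify the effect size for the treatment program on each of the secondary outcomes assessed". Mean and variability are the only free-standing glycemic outcomes in that list.

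The covariates are given under Aim 1: "Each model will include the baseline outcome covariate as well as additional disease covariates including diabetes technology use and length of diagnosis". Mean glucose is not among them, and no model of SDBG given MBG is described for Aim 2. The SAP deals only with active minutes and adds nothing here.

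**The concern.** MBG and SDBG are computed from the same readings. For a positive, right-skewed quantity, spread often rises with level. Where it does, a treatment that only lowers the level also lowers the SD, and two Aim 2 effect estimates would then carry one signal. The reverse can also happen: a real change in relative variability can be masked in SDBG when the mean moves the other way.

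What is at stake is the reading of the glycemic results. A fall in both MBG and SDBG could be reported as an effect on level and an effect on stability when the data show only the first. Time-in-range does not settle it, because it is limited to CGM users and reflects both level and spread.

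**Working it through.** The plan states no figure that depends on the choice of index, so there is nothing to reproduce. The question is how large the overlap could be, and whether adding CV would expose it.

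**Inputs from the Protocol.** Variability index SDBG; MBG as a separate outcome from the same seven days; 60 participants; anticipated Aim 2 effects of d = 0.4 to 0.8.

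**Inputs assumed, because the documents give none.** A fall in mean glucose of 5% to 10%; a between-person SD of SDBG equal to 20% to 35% of its average; 30 per arm; two-sided 0.05.

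**Step 1: constant relative variability.** With SD = CV × mean and CV fixed, the percentage change in SD equals that in the mean. As an example, take an assumed mean of 180 to 220 mg/dL, a CV of 0.35 to 0.45 and a fall of 20 mg/dL. The SD then falls by 20 × 0.35 = 7 to 20 × 0.45 = 9 mg/dL. In percentage terms that is 20/220 = 9% to 20/180 = 11%, the same as the mean.

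**Step 2: on the standardized scale.** Apparent d = (percentage fall in SDBG) / (between-person SD of SDBG as a percentage of its average).

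| Fall in mean | Between-person SD 20% | 25% | 35% |
|---|---|---|---|
| 5% | 0.25 | 0.20 | 0.14 |
| 10% | 0.50 | 0.40 | 0.29 |

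The range is 0.14 to 0.5. Its upper end overlaps the lower part of the anticipated 0.4 to 0.8.

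**Step 3: how far this depends on proportionality.** Trials of 30 per arm were simulated (1,500 per setting), with treatment shifting only the mean. Each follow-up outcome was regressed on its baseline value and arm. Assumed values: mean 200 mg/dL, between-person SD 40, CV 0.40 with SD 0.06, baseline correlation 0.6. The table gives the share of trials with a significant effect.

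| Relation of SD to mean | Outcome | Mean shift d = 0.4 | 0.7 | 0.8 |
|---|---|---|---|---|
| Proportional | SDBG | 34% | 77% | 86% |
| Proportional | CV | 4% | 6% | 6% |
| Independent | SDBG | 5% | 5% | 5% |
| Independent | CV | 30% | 73% | 84% |

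In these settings a shift of d = 0.4 is 0.4 × 40 = 16 mg/dL, or 16/200 = 8% of the mean. That column therefore lies inside the 5% to 10% range of Step 2. The other two are falls of 14% and 16%, outside it.

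**Step 4: reading the pair.** Each index alone misleads under one relation and behaves under the other. Both can be significant no more often than the rarer of the two. From the table, that caps a joint false signal at about 6% under proportionality (set by CV) and about 5% under independence (set by SDBG).

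**The case against.** A reader might infer that the SD necessarily scales with the mean, so that any fall in mean glucose would be counted twice. The documents do not support this. They report no glucose mean, SD, CV or relation between them, and under independence SDBG stays at its nominal 5%.

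A reader might also infer that SDBG is the wrong index and that CV should take its place. That does not follow either. A lower SD is a real reduction in absolute spread. CV has the mean in its denominator, so if the SD does not depend on the mean, CV shows a change that did not occur (30% to 84% of simulated trials). Replacement would exchange one unverified assumption for another.

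Three further points have force.

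- The Protocol nowhere says SDBG will be read as evidence independent of MBG. Aim 2 is exploratory, and reporting correlated secondary outcomes is not an error.
- The artefact is modest. Without baseline adjustment, at 30 per arm and two-sided 0.05, power is about 12% at d = 0.2 and 34% at d = 0.4.
- CV can be computed later from data already collected.

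All three keep the point small. The last does not remove it, because an index chosen after the results are known is weaker than one named beforehand.

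SDBG adjusted for MBG is an alternative. In the same simulation it stayed at 4% to 6% under both relations. It conditions on a post-randomization measure, however, so its coefficient is not a plain treatment effect.

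**Conclusion.** The point holds in a conditional form and is a low-cost improvement. SDBG is the only variability index named, mean and variability each receive their own Aim 2 effect estimate from the same readings, and nothing planned separates them. If SD moves roughly in proportion to the mean, a change in mean glucose could be partly counted again as a change in variability. The size is an apparent d of about 0.14 to 0.5, resting on an assumed 5% to 10% fall in the mean, constant CV, and an assumed between-person SD of SDBG of 20% to 35% of its average.

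The plan is not shown to double count, and SDBG remains a valid measure of absolute spread. No primary outcome, sample size or stated power figure is affected.

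**What to change.** Keep SDBG as planned. In item 22 and the Aim 2 analysis text, add CV = SDBG/MBG for each adolescent at baseline and follow-up as a companion variability outcome in the same model. Add a reading rule such as:

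> Effects on MBG, SDBG and CV will be reported together with confidence intervals. A treatment effect on variability distinct from mean glucose will be claimed only if SDBG and CV move in the same direction.

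Direction is best judged from the estimate with its interval and not from the sign alone. Under proportionality the true CV effect is nil, and its sign would often match that of SDBG by chance.

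The rule covers relations from none to proportional. If SD rose more than proportionally with the mean, SDBG and CV would both fall with it, which is why MBG should stand beside them in the table.

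The cost is one derived variable, two sentences, and one more exploratory outcome to report. The rule is also somewhat conservative, since a real change seen in only one index would be described but not claimed. No new data or participant burden is involved.
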